5.2 Exclusion Criteria

- Paroxysmal or persistent AF where only standard PVI is planned.
- Mechanical mitral valve
- Presence of intracardiac thrombus or contraindication to systemic anticoagulation
- Any medical condition or anatomical contraindication that, in the investigator's judgment, precludes safe participation.
- Pregnant women
- Ability and willingness to provide written informed consent.

6. STUDY PROCEDURES

6.1 Pre-Procedural Management

1. Class I and Class III antiarrhythmic drugs will be discontinued at least 3 days prior to the procedure, with amiodarone discontinued at least 2 weeks prior when feasible. Beta blockers and Calcium channel blockers are allowed.
2. Oral anticoagulation will be maintained uninterrupted according to guideline-based practice.
3. Intracardiac thrombus will be excluded by transesophageal echocardiography, cardiac CT or intracardiac echocardiography prior to the procedure, according to institutional practice.

6.2 Intra-Procedural Workflow

The procedure will be performed under general anesthesia. Following standard venous access, transseptal puncture will be performed to access the left atrium. Systemic anticoagulation with intravenous Heparin will be administered and maintained to achieve an activated clotting time (ACT) >300 seconds.

• Phase 1: Voltage Mapping (coronary sinus pacing)

Following transseptal access and prior to ablation, a left atrial 3D map using TPI with left atrial voltage mapping will be performed using the Octaray catheter. The Octaray catheter will then be exchanged for the Optrell catheter, and a second high-density voltage map will be acquired on the

same 3D map (remap). A high density Multipolar map using parallel mapping will be performed in the same time with the Optrell catheter. All the maps need to have a fill threshold $\leq 3\text{mm}$ to allow sufficient density.

For patient in atrial fibrillation, an electrical cardioversion will be performed and mapping will be performed during coronary sinus pacing. For patient in sinus rhythm, mapping will be performed during coronary sinus pacing. For patient in atrial flutter, mapping will be performed in arrhythmia.

• **Phase 2: Ablation:**

The operator will perform PVI and any clinically indicated linear lesion sets according to standard of care using either radiofrequency or pulsed field ablation energy.

• **Phase 3: Conduction Block Assessment**

After completing the ablation phase, conduction block across lines will be assessed using both methods:

- *Optrell Vector Assessment*: Real-time evaluation of conduction vectors using the Optrell catheter and V8 software. The time to determination, from the beginning of the mapping (pacing start) to block confirmation, and the binary result (block vs. no block) will be recorded.
- *Standard Activation Mapping*: Creation of a full activation map using the Octaray catheter (often requiring pacing maneuvers) to establish the gold-standard confirmation of block. Time to determination, from the beginning of the mapping to block confirmation, and the binary result will be recorded.

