4.2 Secondary Endpoints

- **Bipolar Voltage Correlation:** Statistical correlation and evaluation of systematic bias (limits of agreement) between the bipolar voltage amplitudes recorded by the two catheters in matched anatomical regions.
- **Multipolar Voltage Correlation:** Statistical correlation and evaluation of systematic bias (limits of agreement) between the multipolar voltage amplitudes recorded by the Optrell catheter and the bipolar voltage amplitudes recorded by the Octaray catheter in matched anatomical regions
- **Clinical Efficacy:** Freedom from any documented atrial tachyarrhythmia lasting ≥ 30 seconds at 1, 3, 6, 9, and 12 months.
- **Safety:** Incidence of acute procedural complications prior to hospital discharge.

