232 Continuation, initiation, or discontinuation of AAD therapy during follow-up will not be dictated
233 by the study protocol. All AAD use will be prospectively documented, including drug type, dosing,
234 changes, discontinuation, and replacement. This information will be incorporated into the clinical
235 database and considered in exploratory analyses of arrhythmia recurrence.

236

237 **7.4 Redo Procedures and Lesion Durability Assessment**

238 Any documented recurrence of atrial flutter or AF will prompt consideration for a redo procedure,
239 as clinically indicated.

240 If a redo procedure is performed during the 12-month follow-up period, the index protocol
241 performed again: a left atrial 3D map using TPI with left atrial voltage mapping will be performed
242 using the Octaray catheter. The Octaray catheter will then be exchanged for the Optrell catheter,
243 and a second high-density voltage map will be acquired on the same 3D map (remap). A high
244 density Multipolar map using parallel mapping will be performed in the same time with the Optrell
245 catheter. All the maps need to have a fill threshold ≤ 3 mm to allow sufficient density. For patient
246 in atrial fibrillation, an electrical cardioversion will be performed and mapping will be performed
247 during coronary sinus pacing. For patient in sinus rhythm, mapping will be performed during
248 coronary sinus pacing. For patient in atrial flutter, mapping will be performed in arrhythmia.

249 • **Block Assessment:** Prior to delivering any new ablation, the operator must re-assess
250 conduction block across all linear ablation lesions created during the index procedure.

251 **Gold Standard Block Assessment:** Creation of a full activation map using the Octaray catheter
252 (often requiring pacing maneuvers) to establish the gold-standard confirmation of block. Time to
253 determination, from the beginning of the mapping to block confirmation, and the binary result will
254 be recorded.

255 **Optrell Vector Assessment:** Real-time evaluation of conduction vectors using the Optrell catheter
256 and V8 software. The time to determination, from the beginning of the mapping (pacing start) to
257 block confirmation, and the binary result (block vs. no block) will be recorded.

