8.2 Efficacy Analyses

• **Concordance of Block:** Agreement between the vector-based assessment and standard activation mapping will be evaluated using absolute percentage agreement and Cohen's Kappa statistic for inter-method reliability.

• **Time to Confirmation:** The time required to confirm conduction block will be compared between the two methods using a paired t-test or Wilcoxon signed-rank test, depending on the normality of the data distribution.

• **Voltage Comparison:** Paired continuous voltage data from the Octaray and Optrell catheters will be analyzed using Pearson or Spearman correlation coefficients. Furthermore, Bland-Altman analysis will be conducted to assess for systematic bias and establish limits of agreement between the two catheter designs.

• **Clinical Outcomes:** Freedom from arrhythmia at 12 months will be analyzed using Kaplan-Meier survival estimates.

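### The voltage maps are always taken in the same order, Octaray then Optrell, so the Bland-Altman mean difference cannot separate catheter from map position

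*Protocol*

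**What the plan says.** Section 6.2, Phase 1, sets one sequence for all patients before ablation. First, "left atrial voltage mapping will be performed using the Octaray catheter". Next, "The Octaray catheter will then be exchanged for the Optrell catheter", and the second voltage map is placed on that same 3D map, as a remap. The multipolar data come from the same pass: "A high density Multipolar map using parallel mapping will be performed in the same time with the Optrell catheter". Both Optrell maps therefore take second position, on a shell built with the Octaray.

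Section 7.4 prescribes the same sequence at a redo procedure: "using the Octaray catheter. The Octaray catheter will then be exchanged for the Optrell catheter".

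Section 4.2 makes the between-catheter difference a secondary endpoint, "Statistical correlation and evaluation of systematic bias (limits of agreement) between the bipolar voltage amplitudes recorded by the two catheters", with a parallel endpoint for Optrell multipolar against Octaray bipolar voltage. Section 8.2 states the analysis: "Bland-Altman analysis will be conducted to assess for systematic bias and establish limits of agreement between the two catheter designs". Section 2.3 gives the purpose, which includes deciding whether each catheter needs its own voltage cutoffs.

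The protocol does not mention alternating, balancing or randomising the order, repeating the Octaray map, or adjusting for order. The Phase 1 mapping table in Appendix D has no field for it.

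**The concern.** A paired comparison removes differences between patients, but not differences between the first and second measurement. Here the first is always one catheter and the second always the other. Anything that changes voltage between the two maps, or that comes from placing points on an existing shell, enters the mean difference as if it were a property of the catheter.

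The protocol's own workflow offers possible sources. Patients in AF are cardioverted before mapping, so the Octaray map is always the one nearer the shock. The Optrell points always go onto an Octaray-built geometry, and the endpoint depends on matching anatomical regions. Time under anaesthesia and catheter manipulation accumulate before the second map.

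At stake is the inference sought in section 2.3. A need for catheter-specific cutoffs follows from the mean difference only if that difference is due to electrode design. More patients or points would not help, and no SAP could recover the information, because no patient has the reverse order.

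**Working it through.** **The plan's own figure.** Section 8.1 targets 30 patients without an SD, effect size, alpha or precision target, so there is no calculation to reproduce. The point does not depend on one; 30 is used below only as the number of patients.

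**Step 1: what can be estimated.** Let *c* be the catheter effect (Optrell minus Octaray) and *p* the position effect (second minus first map). Under the protocol's order, every patient's expected difference is *c + p*.

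- Fixed order: a within-patient model with 30 patient effects, catheter and position has 32 columns but rank 31. The catheter and position columns are identical, so only *c + p* is estimable.
- 15/15 order: the rank is 32 of 32. The expected differences are *c + p* (Octaray first) and *c − p* (Optrell first), and their average is *c*.

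**Step 2: which summaries are affected.** Adding a constant *p* to every difference moves the mean and both limits of agreement by *p*. The SD of the differences, and so the width of the limits, does not change. Nor does the correlation coefficient.

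**Step 3: illustrative size.** The documents give no drift, so it is assumed, as *k* times the SD of the patient-level difference. The nominal 95% interval for the mean bias uses t(0.975, 29) = 2.045. Its coverage is P(|T| < 2.045), where T is noncentral t with 29 df and noncentrality *k*√30.

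| Drift *k*, all 30 patients | Noncentrality | Coverage |
|---|---|---|
| 0.1 | 0.548 | 91.7% |
| 0.2 | 1.095 | 81.5% |
| 0.3 | 1.643 | 64.5% (0.6445) |
| 0.5 | 2.739 | 24.6% |

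With no true catheter difference, 20,000 simulated trials per setting gave a false finding by paired t-test in 5.1%, 8.6%, 26.3% and 75.6% of trials at drifts of 0, 0.1, 0.25 and 0.5 SD. With 15/15 order and the two-sequence contrast, the rate stayed between 5.0% and 5.3%.

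**Step 4: drift in cardioverted patients only.** The number cardioverted is not in the documents, so 10 and 15 of 30 are assumed. A 0.5 SD drift then shifts the mean by 0.5 × 10/30 = 0.167 SD or 0.5 × 15/30 = 0.25 SD. Simulated coverage is about 87% and 76%. At 0.1, 0.2 and 0.3 SD it is about 95%, 94% and 92% with 10 affected, and 94%, 92% and 88% with 15.

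**Step 5: price of balancing.** The standard error is 1/√30 = 0.183 SD with fixed order, and ½√(1/15 + 1/15) = 0.183 SD with 15/15. The 95% half-widths are 2.045 × 0.1826 = 0.373 SD (29 df) and 2.048 × 0.1826 = 0.374 SD (28 df).

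**Step 6: what balancing does not remove.** If the position effect is *p* when the Optrell is second and *p′* when the Octaray is second, the averaged estimate is *c + (p − p′)/2*. A shell effect that differs by catheter leaves half its difference behind.

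**The case against.** The strongest reply is that no drift has been shown. Both maps are taken before ablation, in the same chamber, under general anaesthesia, and under coronary sinus pacing for patients in AF or sinus rhythm. Section 9.2 puts the whole study-related prolongation at about 15 minutes. This stands: the design fails to identify the catheter effect, but that does not make the distortion large.

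Time since shock concerns only cardioverted patients. This also stands, and it is why the 25% figure must not be read as the expected consequence of that mechanism.

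A comparison of the catheter difference between cardioverted and other patients could probe the shock-related part. That is partly right. It says nothing about a drift common to all patients, and Appendix D has no field for rhythm at mapping or for cardioversion at the procedure.

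One shared shell may also help the matching of regions, and section 8.2 sets no cutoff or decision rule that a small shift would overturn. Both are fair, but neither separates catheter from position.

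A reader might infer that the whole voltage comparison is invalid. The documents do not support that: the correlation and the width of the limits withstand a constant shift. A reader might also extend the point to the primary endpoints, but it concerns only the voltage maps, not block concordance or time to confirmation. Section 3.2 also names a comparison after ablation, but section 6.2 describes no voltage maps for it and no order, and section 6.3 assigns the paired voltage comparison to the pre-ablation sequence.

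**Conclusion.** The point holds for the mean difference, and hence the position of the limits of agreement, in both secondary voltage endpoints (bipolar and multipolar). Under the stated order these estimate catheter effect plus position effect, and no analysis of the data can isolate the catheter effect.

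The size is unknown. The coverage figures rest on assumed drifts in SD units, on a patient-level mean interval that the protocol does not itself specify, and, for the largest losses, on a drift shared by all 30 patients. They show sensitivity and are not a forecast. The change is worth making because it is cheap and cannot be made after the data are collected. It is not a reason to doubt the primary endpoints.

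**What to change.** In section 6.2, Phase 1, balance the order of the two pre-ablation voltage maps 1:1: 15 patients Octaray first and 15 Optrell first, from a prepared list, with the first catheter building the shell. Bring section 7.4 into line. Add an order field to the Phase 1 tables in Appendices D and F. In section 8.2, estimate the catheter bias as the average of the two sequence-specific mean differences, and report those two differences as well. State that this removes an additive position effect but not a shell effect that differs by catheter; a marked gap between the sequence-specific differences shows that position or shell matters.

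The cost is a 30-line list, one CRF field and one analysis term, with no extra patient, map or exchange and a half-width of 0.374 instead of 0.373 SD. The downsides are that the Optrell comes first and builds the shell in half of the patients, and that sections 6.2 and 6.3 need an amendment, including a check that the observational description still fits.

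If the sponsor keeps one fixed order, state the confounding in the protocol and the report. In that case the mean difference should not be attributed to electrode design, and catheter-specific cutoffs should not rest on it alone.

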4. STUDY ENDPOINTS

4.1 Primary Endpoints

- **Concordance:** Percentage of agreement (presence vs. absence of bidirectional block) between the Optrell real-time vector assessment and standard activation remapping on a per-line basis.
- **Workflow Efficiency:** Difference in time (in minutes) required to confirm conduction block status using the Optrell vector method versus full activation mapping.

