Variable	Data Entry
Date of Procedure	_____
Patient MRN	_____
Age / Gender	_____ years  Male  Female
Height	_____ cm
Weight	_____ kg
BMI	_____ kg/m ²
Type of Arrhythmia	 Paroxysmal AF  Persistent AF  Atrial Flutter : _____
Prior AF Ablation?	 No (De novo)  Yes (Redo) : _____
Operator 1 Operator 2	

CHA2DS2-VASc Score

Risk Factor	Points	Check if Present
Congestive Heart Failure	1	
Hypertension	1	
Age ≥75 years	2	
Diabetes Mellitus	1	

CONFIDENTIAL

Risk Factor	Points	Check if Present
Stroke / TIA / Thromboembolism	2	
Vascular Disease	1	
Age 65 - 74 years	1	
Sex Category (Female)	1	
TOTAL SCORE		____ / 9

Echocardiography Parameters

Variable	Entry
Date of Echo	____ / ____ / ____
LVEF (%)	_____
LA Diameter (mm)	_____
LA Volume (ml)	_____
LA Volume Indexed (ml/m ²)	_____
RA Enlargement	 None  Mild  Moderate  Severe
Mitral Regurgitation	 None  Mild  Moderate  Severe

Antiarrhythmic Drug (AAD) History

(Check all currently or recently used)

☐ Amiodarone ☐ Flecainide ☐ Propafenone ☐ Dronedarone ☐ Other: _____

SECTION 2: PHASE 1 - PRE-ABLATION MAPPING

(Both maps must be acquired during CS pacing or in arrhythmia if patient is in flutter, with a fill threshold 3mm)

Catheter	LA Map Completed?	Fill Threshold \leq 3mm Achieved?	Total Number of Points
Octaray	 Yes  No	 Yes  No	_____ points
Optrell bipolar	 Yes  No	 Yes  No	_____ points
Optrell multipolar	 Yes  No	 Yes  No	_____ points

Catheter	RA Map Completed?	Fill Threshold \leq 3mm Achieved?	Total Number of Points
Octaray	 Yes  No	 Yes  No	_____ points

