Optrell bipolar	 Yes  No	 Yes  No	_____ points
Optrell multipolar	 Yes  No	 Yes  No	_____ points

SECTION 3: PHASE 2 - ABLATION DETAILS

Variable	Data Entry
Ablation Energy Used	 RFA  PFA
PVI Performed?	 Yes  No
PVI Successfully Achieved?	 Yes  No
First Pass Isolation ?	 Yes  No
Linear Lesions Created (Check all that apply)	 Roof Line  Posterior Wall Isolation (PWI)  Cavotricuspid Isthmus (CTI)  Mitral Isthmus Line  Other: _____

SECTION 4: PHASE 3 - CONDUCTION BLOCK ASSESSMENT

(Complete this sub-section for EVERY linear lesion created. See Section 4b, 4c and 4d. Duplicate if necessary.)

Line Checked	 Roof Line  Posterior Wall Isolation (PWI)  Cavotricuspid Isthmus (CTI)  Mitral Isthmus Line  Other:	
Ablation Energy Used	 RFA  PFA	

Assessment Method	Time to Verify Block	Block Confirmed?
Optrell Vector Assessment (time to assess block by moving the catheter across the line to review vectors)	___ min : ___ sec	 Yes  No
Octaray Activation Mapping (time to create an activation map sufficient to determine presence or absence of block)	___ min : ___ sec	 Yes  No

Concordance for this line: ☐Yes (Methods agree) ☐No (Methods disagree)

Explain:_____

SECTION 5: ACUTE PROCEDURAL COMPLICATIONS (completed at hospital discharge)

Variable	Data Entry
None	
Pericardial Effusion / Tamponnade	
Stroke / TIA	

CONFIDENTIAL

Variable	Data Entry
Vascular Complication requiring intervention	
Phrenic Nerve Injury	
Prolongation of Hospitalization (>24 hours beyond the expected post-procedural course)	
Esophageal injury	

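### Both primary endpoints rest on two readings of the same line, but the protocol sets no order, does not lock the first call and does not mask the second

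*Protocol*

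**What the plan says.** Section 4.1 defines two primary endpoints. The first is "Percentage of agreement (presence vs. absence of bidirectional block) between the Optrell real-time vector assessment and standard activation remapping on a per-line basis". The second is "Difference in time (in minutes) required to confirm conduction block status using the Optrell vector method versus full activation mapping".

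Both are obtained in section 6.2 Phase 3: "After completing the ablation phase, conduction block across lines will be assessed using both methods". Two bullets follow, Optrell vectors and then the Octaray reference, described as "Creation of a full activation map using the Octaray catheter (often requiring pacing maneuvers) to establish the gold-standard confirmation of block". No word makes the list a sequence. Section 7.4 repeats both assessments at a redo procedure during follow-up, and there the reference comes first: "Gold Standard Block Assessment: Creation of a full activation map using the Octaray catheter".

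The order in which the methods are listed is:

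| Place | Listed first | Listed second |
|---|---|---|
| 6.2 Phase 3 | Optrell | Octaray |
| Appendix D, Sections 4 to 4d (index CRF) | Optrell | Octaray |
| 7.4 (redo text) | Octaray | Optrell |
| Appendix F, Sections 3 and 5 with sub-sections (redo CRF) | Optrell | Octaray |

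Each per-line form holds both calls, both times and a tick box headed "Concordance for this line". It has no field for which method came first or who made each call. Section 1 of Appendix D has an entry "Operator 1 Operator 2" for the procedure as a whole, not for each reading. Nothing in the protocol mentions masking, an independent reader, alternation, or locking the first result. Section 9.2 says that gaps found are treated at once, without saying whether the second reading has been made by then.

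**The concern.** The study asks whether vectors alone would give the answer that a full remap gives. That needs a vector call that owes nothing to the remap and a reference call that owes nothing to the vectors. With two readings of one line in one session, only the conduct rules can secure this, and the protocol gives none.

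Three mechanisms follow:

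- A second call made with knowledge of the first can be drawn toward it, which raises agreement.
- A gap treated between the readings changes the line, so the two calls describe different lesion states, which lowers agreement.
- The second method may benefit from the pacing set-up and from what the first showed about suspected gaps, which shortens its time.

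The percentage agreement, kappa and paired tests of section 8.2 cannot restore independence lost in the laboratory. Nor can order be adjusted for later if it was never recorded.

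**Working it through.** The protocol gives no figure to reproduce here. The target of 30 patients comes without calculation inputs, and the point does not depend on it. Every accuracy, prevalence, pull and time value below is an assumption used to show scale.

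**1. Pull toward the first call.** Let p be the share of lines blocked on the reference, Se the probability that vectors call a blocked line blocked, and Sp the probability that they call an unblocked line unblocked. With independent readings, agreement = p·Se + (1−p)·Sp. If a share c of disagreements is pulled to the first call, agreement = 1 − (1−c)·(1 − independent agreement). Kappa = (agreement − chance)/(1 − chance).

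*Case A: p = 0.70, Se = 0.90, Sp = 0.70.*
- Independent: agreement 0.63 + 0.21 = 0.84. The block margins are 0.70 and 0.72, so chance = 0.504 + 0.084 = 0.588 and kappa = 0.252/0.412 = 0.61.
- c = 0.5: agreement 1 − 0.5 × 0.16 = 0.92. With vectors first, the margins are 0.71 and 0.72, chance = 0.5924 and kappa = 0.3276/0.4076 = 0.80. With Octaray first, kappa = 0.336/0.416 = 0.81.

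*Case B: p = 0.80, Se = 0.95, Sp = 0.80.*
- Independent: agreement 0.76 + 0.16 = 0.92. Both margins are 0.80, chance = 0.68 and kappa = 0.24/0.32 = 0.75.
- c = 0.5: agreement 0.96 and kappa = 0.28/0.32 = 0.875, in either order.

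In this model the rise in agreement is the same whichever method goes first. Alternating the order does not remove it.

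**2. Gap treatment between readings.** Take Case B with vectors first, and let a share g of the gaps found by vectors be treated successfully before the second reading. Lines that both methods would have called unblocked then become disagreements: agreement = p·Se + (1−p)·Sp·(1−g). For g = 0.5 this is 0.76 + 0.16 × 0.5 = 0.84, down from 0.92. With p = 0.70 it is 0.665 + 0.24 × 0.5 = 0.785, down from 0.905.

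In Case B, pull alone at c = 0.5 adds 4 points and treatment alone at g = 0.5 removes 8. The net sign depends on c and g, which the protocol leaves open.

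**3. Time carry-over.** Let D be the true difference (activation minus vector) and s the minutes saved by whichever method is second. Take D = 5 and s = 2.
- Vectors always first: 5 − 2 = 3 min.
- Octaray always first: 5 + 2 = 7 min.
- Balanced order: (3 + 7)/2 = 5 min. This cancels only if the saving is equal for both methods and lines are balanced across orders.

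**The case against.** The strongest reply is that the protocol never says that the second reader knows the first result. Phase 3 is written in the passive voice, and a shared form shows where results are recorded, not when or by whom they were called. This stands. A reader might infer that the operators know the first result, but that is an inference from silence, real-time reading and a common form. What the document does show is that nothing prevents it.

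A reader might also conclude that concordance is inflated. Section 9.2 tells against that, because treating a gap between readings would lower agreement. Only the statement that it can be inflated is supported.

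If the listed order at index were followed, the vector call would come before the reference, and any time carry-over would shorten the Octaray time, against the study's own hypothesis. That is true, but the order is listed, not required.

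At redo, a reader might infer that the sequence is reversed and the reference already seen when vectors are read. The reversal is in the 7.4 text only, because the redo CRF keeps Optrell first. The earlier Octaray map in 7.4 is a left atrial voltage map, distinct from the full activation map that serves as reference. Nor does the protocol say that redo lines enter the primary endpoints, so harm by that route is conditional.

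Finally, more dramatic figures are available. Assume 85% independent agreement with both methods calling 90% of lines blocked. Halving the disagreements then lifts kappa from 0.03/0.18 = 0.17 to 0.105/0.18 = 0.58. But that table has vectors detecting only 2.5 of every 10 unblocked lines, so it is a poor guide to scale.

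**Conclusion.** The point holds as a gap in conduct rules that exposes both primary endpoints, not as a demonstrated inflation. Order, locking and masking are unspecified, neither order nor reader is recorded for a line, and 7.4 disagrees with its own CRF.

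Under the assumptions above, pull toward the first call could add 4 to 8 percentage points of agreement and raise kappa by about 0.125 to 0.20. Treatment between readings could remove 8 to 12 points. A 2 min carry-over would move a 5 min difference to 3 or 7 min. The net direction is undetermined. The point should be settled before enrolment, because lost independence and an unrecorded order cannot be recovered in the analysis.

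**What to change.** Amend 6.2 Phase 3, 7.4 and Appendices D and F as follows:

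- (a) For each line, enter, time-stamp and lock the first method's call and time before the second catheter is used. This protects the first call. It does not by itself protect the second.
- (b) Alternate which method goes first by study number, under the same rule at index and redo. Align the 7.4 text with the redo CRF. Record order and reader for each line.
- (c) Where a second operator is already present, have that operator make the second call without being told the first. Otherwise record that the second call was unmasked, and report agreement by order. That is disclosure, not correction.
- (d) Derive concordance from the two locked calls instead of an operator's tick.
- (e) Reconcile 6.2 with 9.2 by stating how the two study readings relate in time to any gap treatment, so that both readings used for concordance refer to the same lesion state. When to treat is a clinical matter on which this point takes no position.

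The cost is protocol wording, a few CRF fields (order, reader, lock time, masked or not) and more discipline in the laboratory. Alternation may affect catheter exchanges, which should be checked against the prolongation of about 15 minutes stated in 9.2. The concordance figure may come out lower.

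### The recording rules for both primary endpoints do not match the block-status endpoints of section 4.1: the clocks stop at confirmed block, and the CRF has no category for an undetermined reading

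*Protocol*

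**What the plan says.** **Endpoints.** Protocol 4.1 defines concordance as "Percentage of agreement (presence vs. absence of bidirectional block) between the Optrell real-time vector assessment and standard activation remapping on a per-line basis" and workflow efficiency as "Difference in time (in minutes) required to confirm conduction block status using the Optrell vector method versus full activation mapping". Both are about status, whichever way it turns out.

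**Recording text.** Section 6.2, Phase 3, records the Optrell time "from the beginning of the mapping (pacing start) to block confirmation, and the binary result (block vs. no block) will be recorded". For Octaray it says "Time to determination, from the beginning of the mapping to block confirmation, and the binary result will be recorded". Section 7.4 repeats both rules for redo procedures. Section 8.2 compares the time needed to confirm block by paired t-test or Wilcoxon signed-rank test, and analyses concordance by percentage agreement and Cohen's kappa.

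**CRF.** The per-line forms (Appendix D, Sections 4 to 4d; Appendix F, Sections 3 to 3d and 5 to 5d) head the time column "Time to Verify Block". The Optrell time is described as "time to assess block by moving the catheter across the line to review vectors" and the Octaray time as "time to create an activation map sufficient to determine presence or absence of block". The result column asks, for each method, whether block was confirmed, with Yes and No boxes. A Yes/No concordance box and a free-text line follow. There is no box for a reading that could not settle the question.

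**The concern.** The study asks whether vector reading can replace a full-chamber remap. Three line-level outcomes bear on that: the vectors show block, the vectors show a gap, or the vectors cannot tell. Lines in the third group would still need a remap, so their share is part of the answer. The CRF collects two outcomes, and No can stand for either of the last two.

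The time endpoint has a related problem. Lines with gaps are expected: section 9.2 presents the detection of small gaps as a benefit of taking part, and 7.4 requires every index line to be reassessed at redo. A clock that ends when block is confirmed has no natural end on such a line. Operators may then stop at different events, or leave the field empty.

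Both are matters of data capture. A SAP can say how undetermined lines are analysed, but it cannot reliably recover a category that was never recorded or a stop time that was never defined.

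**Working it through.** The protocol gives no figure to reproduce here. Section 8.1 states 30 patients, with no number of lines, expected agreement or expected time difference. The check is a comparison of wording, followed by an illustration on assumed inputs.

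**Step 1: the clocks side by side.**

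| Place | Start | Stop | Defined for a line with a gap? |
|---|---|---|---|
| 4.1 | not stated | status confirmed | yes |
| 6.2 and 7.4, Optrell | start of mapping, glossed as pacing start | block confirmed | not if read literally |
| 6.2 and 7.4, Octaray | start of mapping, no pacing anchor | block confirmed | not if read literally |
| 8.2 | not stated | block confirmed | not if read literally |
| CRF, Optrell | not stated | block assessed | unclear |
| CRF, Octaray | not stated | presence or absence determined | yes |

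Only the Octaray CRF line defines a stop for either result. Only the Optrell text ties the start to pacing, although 6.2 says that the Octaray map often needs pacing manoeuvres. The two halves of a paired comparison therefore carry different wording at both ends.

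If each of the 30 patients contributed two lines (60 lines, assumed) and 80% to 95% were blocked (assumed), the lines without block would number 60 × 0.05 = 3 to 60 × 0.20 = 12.

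**Step 2: the result field, simplest case.** Assume 60 lines, 90% blocked on Octaray (54 blocked, 6 with gaps), 10% of vectors unreadable regardless of status, every readable vector correct, and unreadable vectors ticked No.

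- Blocked lines: 54 × 0.10 = 5.4 counted as disagreement; 48.6 agree.
- Gap lines: 6 × 0.10 = 0.6 counted as agreement with no gap having been shown; all 6 agree.
- Observed agreement: (48.6 + 6)/60 = 54.6/60 = 91%.
- Optrell marginals: Yes 48.6/60 = 0.81; No 11.4/60 = 0.19.
- Chance agreement: 0.90 × 0.81 + 0.10 × 0.19 = 0.748.
- Kappa: (0.91 − 0.748)/(1 − 0.748) = 0.162/0.252 = 0.64.

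On readable lines alone, agreement is 100% and kappa 1.0. A method that read every line but miscalled 5.4 blocked lines as unblocked would give the identical 2×2 table. The form cannot separate the two.

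**Step 3: with imperfect readings.** Let p be the share of lines blocked and u the share unreadable. Assume readable vectors call 97% of blocked and 90% of unblocked lines correctly. With unreadable scored as no block, agreement is 0.97p(1 − u) + (1 − p)[0.90(1 − u) + u]. For p = 0.90, u = 0.10 this is 0.786 + 0.091 = 0.877. Agreement and kappa:

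| Blocked | Unreadable left out | 5% scored as no block | 10% scored as no block |
|---|---|---|---|
| 80% | 95.6%, 0.86 | 91.8%, 0.76 | 88.0%, 0.68 |
| 90% | 96.3%, 0.81 | 92.0%, 0.65 | 87.7%, 0.53 |
| 95% | 96.7%, 0.71 | 92.1%, 0.50 | 87.5%, 0.37 |

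Agreement falls by about 4 to 9 points and kappa by 0.10 to 0.34. None of these rates comes from the protocol.

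**The case against.** The strongest reply is that the intent is clear. Section 6.2 does record a binary result of block or no block, and both 6.2 and 7.4 call the measured quantity a time to determination. Read with 4.1, the Yes/No box means block or no block, and the stop phrase is loose drafting. Much of this stands. A reader might infer that neither primary endpoint is recorded as status, or that gap lines can have no valid time. The documents do not support either. For concordance, the defect is the CRF label and the missing category. For time, it is contradictory wording, with the Optrell stop on an unblocked line left undefined.

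A reader might also infer that an unreadable vector is scored as no block. No section says so. An operator could leave the box blank, repeat the reading, guess, or use the free-text line. The figures above therefore show what follows if No is ticked. The free-text line helps only partly: it is unstructured, and nothing prompts an entry when an unreadable vector happens to match an Octaray No.

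A third tempting inference is bias in favour of Optrell. The arithmetic does not bear it out: in Step 2, 5.4 lines move against Optrell and 0.6 in its favour. For time, the stop phrase in 6.2 is the same for both methods, so a gap line might drop out as a pair, with unknown effect.

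**Conclusion.** The point holds as a mismatch between status-based endpoints and recording rules that are worded around confirmed block, together with a missing category for undetermined readings. What is lost is interpretability: the share of lines that the vectors cannot read is not captured, and failed readings cannot be told from misreads. Under the Step 2 assumptions the reported result would be 91% and kappa 0.64 for a method that is always right when readable. The size depends on an unreadable rate and a coding habit that the protocol does not give. The direction of any net bias in agreement or time is not established.

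**What to change.** 1. In 6.2, 7.4, 8.2 and Appendices D and F, use one clock for both methods: start at pacing start for that assessment, and stop when status is called, whichever result.
2. On every per-line form, replace the Yes/No result with three boxes for each method: block, no block (gap shown), not determinable.
3. Report the not-determinable rate for each method. Count a not-determinable vector reading as non-agreement in the primary percentage agreement, and show agreement and kappa on determinable lines alongside.
4. An analysis that adds the remap time to the Optrell time on not-determinable lines would turn the 4.1 endpoint into a comparison of strategies. It belongs among the sensitivity analyses only.

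The cost is one extra tick-box per method and matched wording, with no added procedure. Reported agreement may look slightly less favourable: in Step 2 it would be 54/60 = 90% instead of 91%. The change needs to be made before data are collected, because the category cannot be reliably reconstructed afterwards.
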